#### 8.3.5 ADVERSE EVENT REPORTING

AEs will be reported to the IRB and NCTrACS within 3 days of their identification.

---

#### 8.3.6 SERIOUS ADVERSE EVENT REPORTING

The study PI will immediately report to the sponsor any serious adverse event, whether or not considered study intervention related, including those listed in the protocol and must include an assessment of whether there is a reasonable possibility that the study intervention caused the event. Study endpoints that are serious adverse events must be reported in accordance with the protocol unless there is evidence suggesting a causal relationship between the study intervention and the event. In that case, the investigator must immediately report the event to the sponsor.

All serious adverse events (SAEs) will be followed until satisfactory resolution or until the site investigator deems the event to be chronic or the participant is stable. Other supporting documentation of the event may be requested by the study sponsor and should be provided as soon as possible.

---

#### 8.3.7 REPORTING EVENTS TO PARTICIPANTS

N/A

---

#### 8.3.8 EVENTS OF SPECIAL INTEREST

N/A

---

#### 8.3.9 REPORTING OF PREGNANCY

N/A

---

### 8.4 UNANTICIPATED PROBLEMS

---

#### 8.4.1 DEFINITION OF UNANTICIPATED PROBLEMS (UP)

The Office for Human Research Protections (OHRP) considers unanticipated problems involving risks to participants or others to include, in general, any incident, experience, or outcome that meets all of the following criteria:

- Unexpected in terms of nature, severity, or frequency given (a) the research procedures that are described in the protocol-related documents, such as the Institutional Review Board (IRB)-approved research protocol and informed consent document; and (b) the characteristics of the participant population being studied;
- Related or possibly related to participation in the research (“possibly related” means there is a reasonable possibility that the incident, experience, or outcome may have been caused by the procedures involved in the research); and
- Suggests that the research places participants or others at a greater risk of harm (including physical, psychological, economic, or social harm) than was previously known or recognized.

#### 8.4.2 UNANTICIPATED PROBLEM REPORTING

The investigator will report unanticipated problems (UPs) to the reviewing Institutional Review Board (IRB) and to the IRB and study sponsor. The UP report will include the following information:

- Protocol identifying information: protocol title and number, PI’s name, and the IRB project number;
- A detailed description of the event, incident, experience, or outcome;
- An explanation of the basis for determining that the event, incident, experience, or outcome represents an UP;
- A description of any changes to the protocol or other corrective actions that have been taken or are proposed in response to the UP.

To satisfy the requirement for prompt reporting, UPs will be reported using the following timeline:

- UPs that are serious adverse events (SAEs) will be reported to the IRB and to the study sponsor within 7 days of the investigator becoming aware of the event.
- Any other UP will be reported to the IRB and to the study sponsor within 7 days of the investigator becoming aware of the problem.
- All UPs should be reported to appropriate institutional officials (as required by an institution’s written reporting procedures), the supporting agency head (or designee), and the Office for Human Research Protections (OHRP) 7 days of the IRB’s receipt of the report of the problem from the investigator.

#### 8.4.3 REPORTING UNANTICIPATED PROBLEMS TO PARTICIPANTS

N/A

### 9 STATISTICAL CONSIDERATIONS

#### 9.1 STATISTICAL HYPOTHESES

- Primary Efficacy Endpoint(s):
  - Degree of concordance between therapists’ feeding therapy recommendations
    - Null Hypothesis: There is no difference in therapists’ feeding therapy recommendations when using v. not using the tool

- Alternative Hypothesis: There is a difference in therapists' feeding therapy recommendations when using v. not using the tool
- Non-inferiority comparison
- Time period: After reading the case study
- Degree of concordance between therapists' referral recommendations
  - Null Hypothesis: There is no difference in therapists' referral recommendations when using v. not using the tool
  - Alternative Hypothesis: There is a difference in therapists' referral recommendations when using v. not using the tool
  - Non-inferiority comparison
  - Time period: After reading the case study
- Degree of concordance between therapists' specific specialist referral recommendations
  - Null Hypothesis: There is no difference in who the therapists recommend referral to when using v. not using the tool
  - Alternative Hypothesis: There is a difference in who the therapists recommend referral to when using v. not using the tool
  - Non-inferiority comparison
  - Time period: After reading the case study
- Secondary Efficacy Endpoint(s):
  - Degree of concordance between therapists' feeding therapy frequency recommendations
    - Null Hypothesis: There is no difference in therapists' feeding therapy frequency recommendations when using v. not using the tool
    - Alternative Hypothesis: There is a difference in therapists' feeding therapy frequency recommendations when using v. not using the tool
    - Non-inferiority comparison
    - Time period: After reading the case study
  - Degree of concordance between therapists' intervention target choices
    - Null Hypothesis: There is no difference in therapists' feeding therapy intervention target choices when using v. not using the tool
    - Alternative Hypothesis: There is a difference in therapists' feeding therapy intervention target choices when using v. not using the tool
    - Non-inferiority comparison
    - Time period: After reading the case study
  - Decision Support Tool Appropriateness
    - Null Hypothesis: The decision support tool is not appropriate.
    - Alternative Hypothesis: The decision support tool is appropriate.
    - Superiority
    - Time period: After using the tool
  - Decision Support Tool Acceptability
    - Null Hypothesis: The decision support tool is not acceptable.
    - Alternative Hypothesis: The decision support tool is acceptable
    - Superiority
    - Time period: After using the tool
  - Decision Support Tool Feasibility
    - Null Hypothesis: The decision support tool is not feasible.
    - Alternative Hypothesis: The decision support tool is feasible.

- Superiority
- Time period: After using the tool

## 9.2 SAMPLE SIZE DETERMINATION

This is a pilot study. Sample size was selected based on available funding and to achieve equal numbers in each group (group 1: case A then case B; group 2: case B then case A) as well as equal numbers of SLPs and OTs per group (group 1: 14 SLP, 14 OT. Group 2: 14 SLP, 14 OT).

## 9.3 POPULATIONS FOR ANALYSES

All participants who completed the full survey will have their data included in analysis. Partial survey responses will not be included.

## 9.4 STATISTICAL ANALYSES

### 9.4.1 GENERAL APPROACH

For descriptive statistics, counts and percentages will be reported.

For inferential tests, two-tailed tests will be used. Test statistics, p-values, and effect sizes will be reported.

Covariates will be assessed to determine if they should be included in the statistical model. These will include years of experience and being an OT v SLP.

Due to the small sample size and categorical variables, only nonparametric tests will be used.

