## 5.5 STRATEGIES FOR RECRUITMENT AND RETENTION

The target sample size is 56 participants with 28 SLPs and 28 OTs. We anticipate one site will be used – UNC Chapel Hill; although the study will be completed virtually by participants. Target enrollment will not be stratified for age, gender, or race/ethnicity for this pilot study, but future studies will control for these variables. Because participants are expected to be practicing in early intervention, participants will be recruited from private practices (which contract with early intervention) and from the early intervention system in North Carolina. Participants will be recruited through web search, the Child Developmental Services Agency, and word of mouth. Potential participants will be emailed through these groups and will be directed to an interest survey where they will complete a screening. If eligible and interested, they will provide their name and email. In the order of entry, the PI will email them a link to the survey.

Because the fields of occupational therapy and speech language pathology are majority female, specific female recruitment is not necessary. For this pilot study, participants will not be specifically selected for race/ethnicity, but this will be pursued in future, larger studies.

Participants who complete the full survey will receive a \$25 gift card as an incentive.

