### 6.3 MEASURES TO MINIMIZE BIAS: RANDOMIZATION AND BLINDING

14 OTs and 14 SLPs will receive case A first; 14 OTs and 14 SLPs will receive case B first. There are two versions of the survey – one where case A is presented first and one where case B is presented first. Providers will be sent the link to the version to which they are assigned.

Assignment will be based on the order of study entry. For example, the first SLP to enroll will receive case A first, the second SLP to enroll will receive case B first, etc. Similarly, the first OT to enroll will receive case A first, the second OT to enroll will receive case B first, etc.

The PI will complete all randomization computations. There will not be blinding. Blinding is considered unnecessary in this case because the researchers will not have direct interaction with participants, participants will complete the full survey and intervention independently without interaction with the researchers.

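### Section 9.4.1 screens covariates for a model the plan never specifies, and the planned chi-square tests ignore discipline, the factor that allocation balances

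*Combined protocol and SAP*

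**What the plan says.** Section 9.4.1 (General Approach) states: "Covariates will be assessed to determine if they should be included in the statistical model". It continues: "These will include years of experience and being an OT v SLP". The same section says that "only nonparametric tests will be used" and that "For inferential tests, two-tailed tests will be used". It gives no significance level and no criterion for including a covariate.

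Section 9.4.2 analyses the first two primary endpoints (feeding therapy yes/no, referral yes/no) separately for each case. Reporting is descriptive, with a chi-square test of tool v no tool if its assumptions are met. The third primary endpoint is descriptive only. Section 9.4.3 treats therapy frequency (three categories) like the yes/no endpoints, keeps therapy targets descriptive, and gives means and standard deviations for the three tool-rating scores. Section 9.4.5 adds a possible Mann-Whitney comparison of baseline experience.

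On design, Section 5.5 says "The target sample size is 56 participants with 28 SLPs and 28 OTs" and Section 6.3 says "14 OTs and 14 SLPs will receive case A first; 14 OTs and 14 SLPs will receive case B first". Assignment alternates by order of entry within each discipline: "the first SLP to enroll will receive case A first, the second SLP to enroll will receive case B first". Section 9.2 gives this balance, with funding, as the basis of the sample size: "Sample size was selected based on available funding and to achieve equal numbers in each group".

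**The concern.** There are two linked gaps.

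First, the covariate sentence has nothing to act on. None of the analyses listed in Sections 9.4.2, 9.4.3 and 9.4.5 takes a covariate as specified. An analyst must either ignore the sentence or choose a model and an inclusion rule after seeing the data. The second course adds an analyst choice that the plan could easily avoid.

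Second, the design uses discipline and the tests drop it. A discipline effect is plausible: the two professions have different training, and the referral list offers each of them as a referral target. If SLPs and OTs have different yes-rates, a test that pools them counts the between-discipline spread as noise, although the balanced allocation has already removed it from the comparison. The result is a test that rejects too rarely. With 28 therapists per condition in each case, there is little power to spare.

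**Working it through.** **Inputs from the documents.** Two sequences x two disciplines x 14 = 56, which reproduces the planned total. Each therapist sees one case without the tool and the other with it. Within one case the comparison is therefore 28 therapists with the tool against 28 different therapists without it, each side being 14 SLPs and 14 OTs. Tests are two-tailed. There is no stated power to reproduce.

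**Assumptions.** Alpha of 0.05; yes-rates by discipline without the tool; a tool effect that multiplies the odds of yes by 4 in both disciplines. For example, 90% has odds 9, which become 36, or 97.3%; 40% has odds 0.667, which become 2.667, or 72.7%.

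**Test statistics.** Let t and u be the yes counts with and without the tool, and p the pooled yes proportion.
- Unstratified chi-square: (t/28 - u/28)² / [p(1 - p) x 2/28].
- Asymptotic CMH, no continuity correction: (sum of a - m/2)² / (sum of V). In each discipline, a is the yes count with the tool, m is the total yes count, and V = 14 x 14 x m(28 - m) / (28² x 27).
- Exact stratified test: conditional on m in each discipline, with outcomes ordered by probability.

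**Hand check of the conservatism.** The chi-square uses variance p(1 - p). Under 14/14 balance the true variance is the average of the within-discipline variances.
- At 90%/40%: p = 0.65, so p(1 - p) = 0.2275. The within-discipline average is (0.09 + 0.24)/2 = 0.165. The ratio is 0.725, the effective critical value is 1.96/√0.725 = 2.30, and the two-sided error is about 2.1%.
- At 80%/40%: 0.24 against (0.16 + 0.24)/2 = 0.20. The ratio is 0.833, the effective critical value is 2.15, and the error is about 3.2%.

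**Exact enumeration** over all outcomes of the four cells of 14. Each entry reads chi-square / asymptotic CMH / exact stratified:

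| Assumed yes-rates in the two disciplines | Type I error, % | Power at odds ratio 4, % |
|---|---|---|
| 50 / 50 | 4.5 / 4.5 / 2.3 | 67 / 66 / 56 |
| 60 / 40 | 4.1 / 4.5 / 2.4 | 65 / 65 / 55 |
| 80 / 60 | 4.7 / 5.0 / 2.5 | 46 / 48 / 35 |
| 80 / 40 | 3.0 / 5.0 / 2.5 | 51 / 56 / 43 |
| 90 / 50 | 3.1 / 5.0 / 2.3 | 39 / 46 / 33 |
| 90 / 40 | 2.3 / 5.0 / 2.2 | 40 / 50 / 36 |
| 80 / 20 | 1.2 / 4.9 / 2.2 | 36 / 53 / 40 |

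The asymptotic CMH test holds close to 5% throughout. It gains 5 to 16 points of power at gaps of 40 points or more, at most about 2 points at a gap of 20, and loses about 1.6 points (67.4% v 65.8%) with no gap. The exact stratified test is less powerful than the plain chi-square in six of the seven rows.

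**If balance is lost.** Only completers are analysed (Section 9.3). With assumed yes-rates of 70/30, 80/20 or 90/50 and no tool effect, a 16/12 v 12/16 discipline split biases the unadjusted difference by 0.06 to 0.09, with type I error of 4% to 5%. An 18/10 v 10/18 split biases it by 0.11 to 0.17, with type I error of 11% to 18%.

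**Sparse tables.** The chance that the smallest expected count in the pooled table falls below 5 is about 29% if the overall yes-rate is 80%, and 95% if it is 90% (assumed rates). Section 9.4.2 names no fallback test.

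**The case against.** The strongest reply is that little depends on these tests. The study is a pilot sized on funding and equal cells, with no power target to miss. Reporting is descriptive first, and the chi-square runs only if its assumptions hold. The power loss is substantial only at gaps of 40 points or more, and no section gives yes-rates by discipline. All of this stands, and it limits the severity. It does not remove the point: p-values and effect sizes are still planned for two primary endpoints and one secondary endpoint, and the covariate sentence still has no model behind it.

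Four stronger readings are tempting, and the documents do not support them.
- A reader might infer that the unstratified test is biased or gives too many false positives. With 14 of each discipline on each side the difference is unbiased, and the type I error is at or below nominal. Inflation needs an assumed severe imbalance among completers, which the replacement of withdrawn participants (Section 7.2) makes less likely.
- A reader might infer that limiting inference to nonparametric tests makes covariate handling impossible. Stratified nonparametric tests exist. The gap is that none is named.
- A reader might infer that discipline is overlooked altogether. It drives the allocation and is listed as a candidate covariate. It is missing only from the specified tests.
- A reader might infer that an exact stratified test is the natural remedy at this sample size. As the main test it would usually have less power than the chi-square it replaced: 56% v 67% with no gap, and 36% v 40% at 90/40.

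**Conclusion.** The point holds at minor to moderate severity. Section 9.4.1 refers to a model and a covariate decision that the later sections do not supply, and the specified tests do not use the discipline balance built into the allocation. While 14/14 balance holds, the cost is conservatism and lost power, not bias. At an assumed 90/40 gap, type I error is 2.3% v 5.0% and power 40% v 50% for the asymptotic CMH test. At 80/40 the figures are 3.0% v 5.0% and 51% v 56%. With no gap they are 4.5% v 4.5% and 67% v 66%. These figures rest on an assumed alpha of 0.05, an assumed common odds ratio of 4, and assumed yes-rates. The existence and size of any discipline gap cannot be established from the documents.

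**What to change.** In Section 9.4.1, delete the covariate-screening sentence and state that inferential tests are stratified by discipline, with the significance level given.

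In Section 9.4.2, for each yes/no endpoint in each case, pre-specify the asymptotic CMH test without continuity correction, stratified by SLP/OT. State the sparse-count criterion in advance and name the exact stratified test as the fallback when it is met. In that role the exact test compares well with its unstratified counterpart, Fisher's test: 36% v 28% power at 90/40, and 56% v 57% with no gap. It should not be the main test.

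In Section 9.4.3, replace the chi-square for frequency with a discipline-stratified rank test, which also uses the order of the categories. That question goes only to therapists who recommend therapy, so cell sizes may fall below 14. Report years of experience descriptively, and show the endpoint percentages by discipline.

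The cost is SAP wording only, since discipline is already known at allocation. The statistical downside is about 1 to 2 points of power if discipline turns out to be unrelated to the answers. The change should be made before any responses are examined.

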### 9.4.2 ANALYSIS OF THE PRIMARY EFFICACY ENDPOINT(S)

For the following primary outcomes: degree of concordance between therapists' feeding therapy recommendations and degree of concordance between therapists' referral recommendations we have categorical data (2 groups – using tool and not using tool; 2 answers – yes or no). This is a repeated measure (therapists answer once for case A and once for case B). Each case will be analyzed separately. Due to the categorical data and small sample, reporting will be descriptive. Chi square tests will also be run if determined to meet the required assumptions. For chi-square tests, p value and effect size will be reported. These will be independent and therefore, adjustment for multiple comparisons will not be pursued.

For the third primary endpoint, degree of concordance between therapists' specific specialist referral recommendations, descriptive statistics will be used due to the multiple categories, small counts, and small sample size. The percentage of therapists recommending a particular provider will be compared among therapists using and not using the tool.

Across all analyses, missing data will be reported but not corrected for due to the small sample size. Participants who did not complete all survey items will not be included in analysis. Adjustment for multiple comparisons is considered unnecessary due to the small sample size and minimal use of inferential statistics.

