## 1 PROTOCOL SUMMARY

### 1.1 SYNOPSIS

Title:	Evaluation of an Interdisciplinary Decision Guide for Infant Feeding Assessment
Study Description:	This study will determine if a decision support tool changes clinical practice recommendations when used by speech language pathologists and occupational therapists. We hypothesize the support tool will change whether providers will recommend specialist referral.
Objectives:	Primary objectives are the degree of concordance in feeding therapy, referral, and specific specialist referral recommendations between therapists using and not using the tool. Secondary objectives include degree of concordance between feeding therapy frequency and therapy target recommendations as well as acceptability, appropriateness, and feasibility of the tool.
Endpoints:	The endpoint is when the provider has finished reading the case study.
Study Population:	56 speech language pathologists and occupational therapists with at least two years of feeding experience and currently practicing in North Carolina
Phase:	N/A
Description of Sites/Facilities Enrolling Participants:	This study will occur through an online survey. Survey recruitment will be based out of UNC-Chapel Hill.
Description of Study Intervention:	The study intervention is a decision support tool, which is a checklist of signs and symptoms of feeding problems.
Study Duration:	The estimated duration is 6 months.

**Participant Duration:** Participants will take about 20 minutes to complete an initial interest survey and then the full survey.

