## 4 STUDY DESIGN

### 4.1 OVERALL DESIGN

This is a randomized crossover pilot study. It will be conducted online through one site, UNC Chapel Hill. The study intervention is the 'Clinical Feeding Tool' also known as the decision support tool. Our hypothesis is that clinicians will change their recommendations for feeding therapy and specialist referral when using the tool compared to when they do not use the tool. Clinicians will be randomly assigned to respond to either Case A or Case B without using the tool (2 groups). Then, they will respond to the other case using the tool. Total participation time is estimated at 20 minutes.

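### For the two yes/no primary endpoints the plan analyses Case A and Case B only separately, so it never estimates the overall tool effect that its hypotheses are about

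*Combined protocol and SAP*

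**What the plan says.** **Hypotheses.** Section 9.1 gives one null and one alternative per endpoint. For referral they are "There is no difference in therapists' referral recommendations when using v. not using the tool" and "There is a difference in therapists' referral recommendations when using v. not using the tool"; the feeding-therapy pair has the same form. Neither mentions a case. The synopsis (1.1) and Section 4.1 also speak of the tool in general: "We hypothesize the support tool will change whether providers will recommend specialist referral" and "Our hypothesis is that clinicians will change their recommendations for feeding therapy and specialist referral when using the tool".

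**Design.** Section 4.1: "Clinicians will be randomly assigned to respond to either Case A or Case B without using the tool (2 groups"; each therapist then answers the other case with the tool. Section 5.5: "The target sample size is 56 participants with 28 SLPs and 28 OTs". Section 6.3: "14 OTs and 14 SLPs will receive case A first; 14 OTs and 14 SLPs will receive case B first". Section 4.2 gives the reason for the crossover: the therapists differ in experience, so each is to be compared with themselves.

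**Analysis.** Section 9.4.2 recognises that each therapist answers twice, then states "Each case will be analyzed separately". Reporting is descriptive first, with chi-square tests if their assumptions hold. Section 3 defines these endpoints through a with-tool against without-tool difference worked out for both cases. Section 9.4.1 specifies two-tailed tests and restricts testing to nonparametric methods. No section names a combined, stratified or within-therapist estimate, or says how to read the hypothesis if the two cases disagree.

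**The concern.** The hypothesis asks one question about the tool, and the analysis returns two answers, one per case. If Case A differs and Case B does not, a reader who needs only one case will say that the tool changes recommendations, and a reader who needs both will say that it does not. The plan does not choose between these readings before the data are seen.

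The crossover was also chosen for its pairing, and the planned analysis does not use it. Each estimate rests on half of the 112 answers (56 therapists × 2 cases). Chance differences between the cases can then be mistaken for a tool effect specific to one case.

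This is not the multiplicity question. Adjusted p-values would still leave two results for one hypothesis.

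**Working it through.** **1. Sample size.** The plan's own figure reproduces: 4 cells × 14 = 2 groups × 28 = 56. Section 9.2 bases it on funding and balance. The plan gives no alpha, power, effect size or expected rate, so those below are assumptions.

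**2. What a by-case comparison compares.**

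| Group | Without tool (first) | With tool (second) |
|---|---|---|
| 1 (n = 28) | Case A | Case B |
| 2 (n = 28) | Case B | Case A |

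Within Case A, group 2 with the tool is compared with group 1 without it. Within Case B the roles are reversed. Both comparisons are between different therapists, 28 against 28.

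**3. Power per case.** Assume two-sided 0.05 and an uncorrected chi-square. For 60% without and 85% with the tool:
- pooled rate 0.725; null SE = √(0.725 × 0.275 × 2/28) = 0.1193
- alternative SE = √((0.60 × 0.40 + 0.85 × 0.15)/28) = 0.1146
- power ≈ Φ((0.25 − 1.96 × 0.1193)/0.1146) = Φ(0.14) ≈ 0.56; exact enumeration gives 0.569

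**4. Chance that exactly one case is significant.** Assume the same true effect in both cases and both tests run. With independent answers the chance is 2 × power × (1 − power). For 60% to 85% this is 2 × 0.569 × 0.431 = 0.49. For 50% to 90% it is 2 × 0.936 × 0.064 = 0.12. Positive correlation between a therapist's two answers makes the two case contrasts negatively correlated, which tends to raise the chance. The ranges below run from latent correlation 0 to 0.5, by simulation.

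| Without → with tool | Power per case | Exactly one case significant |
|---|---|---|
| 50% → 60% | 0.11 | 0.19–0.21 |
| 50% → 70% | 0.33 | 0.44–0.51 |
| 50% → 75% | 0.49 | 0.50–0.60 |
| 60% → 85% | 0.57 | 0.49–0.58 |
| 70% → 90% | 0.47 | 0.50–0.58 |
| 50% → 80% | 0.67 | 0.44–0.51 |
| 50% → 85% | 0.83 | 0.28–0.31 |
| 50% → 90% | 0.94 | 0.12–0.13 |

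**5. A combined contrast.** Let τ be the tool effect, c the Case B minus Case A difference and π any effect of coming second. The mean within-therapist difference (tool minus no tool) is τ + c + π in group 1 and τ − c + π in group 2. Their average is τ + π. The case effect cancels and the order effect does not.

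The point estimate equals the simple mean of the two by-case differences. The pairing supplies the correct standard error. For 60% to 85% with zero correlation:
- SE = √(¼ × 2 × 0.3675/28) = 0.0810, where 0.3675 = 0.24 + 0.1275
- 0.25/0.0810 = 3.09; power ≈ Φ(3.09 − 2.00) ≈ 0.86

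Simulation (40,000 trials per scenario, t test on 54 degrees of freedom, correlation 0 to 0.5) gives:

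| Without → with tool | Per case | Combined |
|---|---|---|
| 60% → 85% | 0.57 | 0.85–0.95 |
| 70% → 90% | 0.47 | 0.77–0.88 |
| 50% → 75% | 0.49 | 0.79–0.91 |

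Under the null (60% in both cases, or 80% in A and 50% in B) the test's size is 0.049–0.051. A Mantel-Haenszel test stratified by case gives similar power at zero correlation: 0.86 for 60% to 85% and 0.78 for 50% to 75%.

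**6. Where the average fails.** If the tool moves Case A from 40% to 80% and Case B from 80% to 40%, each case has 88% power, but the combined test rejects only about 5% of the time.

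**The case against.** The best defence is that this is a pilot sized on funding. Its reporting is descriptive, its chi-square tests are conditional, and it declares no alpha or success criterion, so no formal decision can flip. By-case analysis also matches Section 3, where the endpoints are defined, and reporting both cases hides nothing. All of this stands and lowers the weight of the point. It does not remove it. Section 9.1 still sets formal hypotheses about the tool, 9.4.1 still promises p-values and effect sizes, and even a descriptive report lacks the overall effect that those hypotheses concern.

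Four stronger readings are tempting and are not supported:

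- *A tool that works equally in both cases gives a split result about half the time.* Under independence, one half is the maximum, reached only near 50% power per case. The documents give no rate or effect that would place the trial there. The figures also assume that both tests are run. If the unstated assumption check is an expected count of 5, both cases qualify in only 51–54% of trials at 70% to 90%, and in 11–15% at 80% to 90%.
- *Every hypothesis is tested only by case.* The third primary endpoint and the therapy targets have no test, and the three tool ratings are summarised once across participants. Among the secondary endpoints, only therapy frequency shares the pattern.
- *Referral should be the sole deciding endpoint because the synopsis hypothesis names it.* The same synopsis lists three primary objectives, as do Sections 3 and 9.1, and 4.1 names feeding therapy as well. Choosing one would be a preference.
- *The combined contrast gives 77–95% power for the tool itself.* The tool always comes second, so this is power for tool plus order. The by-case contrasts carry the same order effect.

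**Conclusion.** The point holds for the feeding-therapy and referral yes/no endpoints. The hypotheses concern the tool, the design rationale is within-therapist, and the only planned analysis is between therapists and by case. There is no overall estimate and no rule for reading disagreement.

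The consequence depends on values that the plan does not give. Under the assumptions in the working, a split result has a probability of about 12% to 60%: 49–58% at 60% to 85%, but 12–13% at 50% to 90%. The power comparison (about 47–57% per case against about 77–95% combined) covers only the three mid-range scenarios. It was computed with a t test, and the power of the nonparametric tests suggested below was not computed. The change is worth making, but the plan is not invalid without it.

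**What to change.** In 9.4.2, for each of the two yes/no primary endpoints:

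- Add one overall with-tool minus without-tool difference, weighting Case A and Case B equally. Estimate it from each therapist's own difference, averaged within each case-order group and then across the two groups. Give a 95% confidence interval that respects the pairing.
- If it is tested, use a nonparametric method, in line with 9.4.1. One option is a permutation test of the same contrast. Because 6.3 assigns by order of entry, that test rests on therapists being exchangeable between groups. Another is a Mainland-Gart test, with case in the role usually held by period.
- Keep the Case A and Case B results alongside. State that one significant and one non-significant case is not by itself evidence of a case-specific effect, and that effects in opposite directions must be read from the case-level results.
- State that the combined and by-case contrasts both include any effect of the tool always coming second.

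The three primary endpoints need not be re-ranked. The cost is SAP wording and one extra analysis of data already collected, with no new participants or survey items. The downside is that an average can hide opposite effects in the two cases, which is why the case-level results stay.
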